17.3 Primary endpoint

The primary objective of this trial is to compare the efficacy of thrice daily BIAsp 30 versus twice daily BIAsp 30, both in combination with metformin, in subjects with type 2 diabetes inadequately controlled on basal insulin combined with OADs.

The primary efficacy endpoint is the change from baseline in HbA_{1c} after 24 weeks of treatment. Change in HbA_{1c} from baseline to the 4, 8, 12, 16, 20 and 24 week’s measurements will be analysed using a Mixed Model for Repeated Measurements (MMRM), with treatment, combination of the two stratification factors (HbA_{1c} value and previous OAD treatment) and region (China/non-China)

as fixed factors and baseline HbA_{1c} as a covariate, all variables nested within visit as a factor. Region China includes China, Hong Kong and Taiwan and non-China includes all the other participating countries. An unstructured covariance matrix will be used to describe the variability for the repeated measurements for a subject. From the MMRM model the treatment difference at week 24 will be estimated and the corresponding 95% confidence interval and p-value will be calculated. All subjects in the FAS will be included in this analysis.

If p-value < 0.05, or equivalently, if the upper bound of the 95% confidence interval is below 0% or the lower bound of the 95% confidence interval is above 0%, the treatment difference will be regarded as statistically significant.

An important assumption for using MMRM is that the missing data are missing at random (MAR).

For this trial, missing data are mainly expected to occur due to withdrawal/discontinuation from the trial. Intermittent missing data (visits with missing data in between visits with data) is expected to be less common.

The main reasons for withdrawal/discontinuation are expected to be ineffective therapy and adverse events. Discontinuation due to ineffective therapy is expected to be MAR to some extent. For missing data due to adverse events, the MAR assumption may be questionable.

Sensitivity analyses will be performed for the primary efficacy endpoint. They will include:

- An analysis of covariance (ANCOVA) model with last observation carried forward (LOCF) imputation. Effects in the model are treatment, combination of the two stratification factors and region as factors, and baseline HbA_{1c} as a covariate.
- A pattern mixture model approach mimicking an ITT scenario where withdrawn subjects are assumed to be switched to the control treatment (i.e., BIAsp 30 BID) after withdrawal. Multiple copies (100 copies) of the full dataset will be generated by imputing missing values based on estimated parameters for the control group. This will be done as follows:
 - In the first step intermittent missing values are imputed using a Markov Chain Monte Carlo method, in order to obtain a monotone missing data pattern. This imputation is done for each treatment group separately and 100 copies of the dataset will be generated.
 - In the second step, for each of the 100 copies of the dataset, an ANCOVA model with combination of the two stratification factors and region as factors and baseline HbA_{1c} and HbA_{1c} at 4 weeks as covariates is fitted to the change in HbA_{1c} from baseline to 8 weeks for the control group only. The estimated parameters, and their variances, from this model are used to impute missing values at 8 weeks for subjects

in both treatment groups, based on their combination of the two stratification factors and region and HbA_{1c} at baseline and 4 weeks.

- In the next steps, for each of the 100 copies of the dataset, missing HbA_{1c} values at 12, 16, 20 and 24 weeks are imputed sequentially in the same way as for 8 weeks. The imputations are based on an ANCOVA model with combination of the two stratification factors and region as factors and the HbA_{1c} values at baseline and previous post-baseline visits as covariates, fitted to the control group.
- After imputation, for each of the complete data sets, the change from baseline to Week 24 is analysed using an ANCOVA model with treatment, combination of the two stratification factors and region as factors, and the baseline HbA_{1c} value as a covariate.
- The estimates and standard deviations for the 100 data sets are pooled to one estimate and associated standard deviation using Rubin's formula:

$$m_{MI} = \frac{1}{100} \sum_{i=1}^{100} m_i, \quad SD_{MI} = \sqrt{\frac{1}{100} \sum_{i=1}^{100} SD_i^2 + \left(1 + \frac{1}{100}\right) \left(\frac{1}{100-1}\right) \sum_{i=1}^{100} (m_i - m_{MI})^2}$$

where m_i and SD_i are the estimated means and standard deviations for the 100 copies of the dataset, and m_{MI} , SD_{MI} are the pooled estimates.

- From m_{MI} and SD_{MI} , the 95% confidence interval for the treatment difference and the associated p-value are calculated.

17.4 Secondary endpoint

17.4.1 Supportive secondary endpoints

17.4.1.1 Efficacy endpoints

The following continuous endpoints are defined:

- Change from baseline in FPG after 24 weeks of treatment (analysed by central laboratory)
- 7-point SMPG profiles after 24 weeks of treatment
 - 7-point SMPG profile
 - Change from baseline in 2-hour PPG and PPG increment at individual meal (breakfast, lunch and main evening meal)

- Change from baseline in mean of 2-hour PPG and PPG increment over 3 main meals (breakfast, lunch and main evening meal)
- Change from baseline in mean of the 7-point profile
- Fluctuation in the 7-point profile

To compare the 7-point SMPG profiles of the two treatments after 24 weeks, a mixed effect model will be fitted to the data. The model will include treatment, time, interaction between treatment and time, combination of the two stratification factors and region as fixed effects. The within-subject residual variance structure will be modelled as 'unstructured'. The time corresponds to planned measurement times during the 24h period. The treatment group by time interaction express whether the profiles of the two treatment groups are parallel over the 7-points. Mean differences between the two treatments and corresponding 95% confidence intervals will be estimated for each time point.

All the other continuous endpoints described above, including change from baseline in FPG and the endpoints derived from 7-point SMPG profile, will be analysed with a similar method as the primary endpoint, where the relevant baseline value will replace baseline HbA_{1c} in the model. The mean of 7-point SMPG profile is defined as the area under the profile divided by the measurement time and is calculated using the trapezoidal method. The fluctuation in the 7-point SMPG profile is defined as

$$\frac{1}{T} \int_0^T |PG(t) - \overline{PG}| dt,$$

where T, PG(t) and \overline{PG} denotes the length of the profile, the PG value at time t and the mean of the profile, respectively. Fluctuation in the 7-point SMPG profile and the relevant baseline value will be log transformed before analysed.

The following dichotomous endpoints are defined:

Subjects who after 24 weeks of treatment achieve (yes/no):

- HbA_{1c} <7.0%
- HbA_{1c} <7.0 % without severe hypoglycaemic episodes
- HbA_{1c} <7.0 % without severe or blood glucose (BG) confirmed hypoglycaemic episodes

The dichotomous endpoints will be analysed by a logistic regression model. Effects in the model are treatment, combination of the two stratification factors and region as factors, and baseline HbA_{1c} as a covariate. The results will include the 95% confidence interval for the odds ratio (BIAsp 30 TID

over BIAsp 30 BID) and the p-value for test of no difference between the groups as part of the presentation.

For the dichotomous endpoint of HbA_{1c}<7% at week 24 (yes/no), missing HbA_{1c} values at week 24 will be imputed using the predicted value from an MMRM analysis. For the other two dichotomous endpoints, as a conservative approach, subjects withdrawn before 24 weeks will be handled as non-responders.

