8.3.1.1 Three times daily self-measured plasma glucose

Subjects will be instructed to perform the following SMPG measurements:

- Before breakfast
- Before lunch
- Before main evening meal

The three times daily SMPG will be performed on 3 random days in the week prior to a clinic visit/phone contact (Visit 3–Visit 26), according to the flow chart in Section [2](#). The plasma glucose value at each time point should be recorded in the diary.

8.3.1.2 7-point self-measured plasma glucose profiles

Subjects will be instructed to perform the following SMPG measurements:

- Before breakfast
- 120 minutes after the start of breakfast
- Before lunch
- 120 minutes after the start of lunch
- Before main evening meal
- 120 minutes after the start of main evening meal
- At bedtime

The 7-point SMPG profile should be performed on the day just prior to Visit 2, Visit 14 and Visit 26, according to the flow chart in Section 2. The plasma glucose value at each time point should be recorded in the diary.

Note that for Visit 14 and Visit 26, both three times daily SMPG and 7-point SMPG profiles are required. In the week prior to these visits, the measurements for both SMPGs may overlap. Since the 7-point SMPG profile includes the following:

- Before breakfast
- Before lunch
- Before main evening meal

these measurements can be used to replace one of the three times daily SMPG values required.

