14.2 Titration Surveillance

An independent Novo Nordisk Titration Group will centrally perform insulin titration surveillance. This is also described in Section [5](#) of the Titration Guideline found in [Appendix A](#).

Surveillance will be performed on an on-going basis throughout the trial. The Novo Nordisk Titration Group reviews the information provided by the investigator in the eCRF after each visit/phone contact and follows-up on significant deviations from the titration guideline.

It is important that information regarding BIAsp 30, dose titration and hypoglycaemic episodes is entered within **24 hours** after the visit/phone contact. Data to be entered are described in Section [8.6.2](#).

15 Data management

Data management is the responsibility of Novo Nordisk.

Appropriate measures, including encryption of data files containing person identifiable data, will be used to ensure confidentiality of subject data, when they are transmitted over open networks.

Data from central laboratories will be transferred electronically. In cases where data is transferred via non-secure electronic networks, data will be encrypted during transfer. The laboratory will also provide all laboratory reports to the investigator for storage at the trial site.

The subject and any biological material obtained from the subject will be identified by subject number and trial ID. Appropriate measures such as encryption or leaving out certain identifiers will be enforced to protect the identity of subjects in all presentations and publications as required by local, regional and national requirements.

16 Computerised systems

Novo Nordisk will capture and process clinical data using computerised systems that are described in Novo Nordisk Standard Operating Procedures and IT architecture documentation. The use and control of these systems are documented.

Investigators working on the trial may use their own electronic systems to capture source data.

17 Statistical considerations

Novo Nordisk will be responsible for the statistical analysis and reporting. Analysis and reporting will be done with data from all sites pooled together.

The statistical analyses will be performed with a significance level of 5% (two-sided tests).

If necessary, a statistical analysis plan (SAP) may be written in addition to the protocol, including a more technical and detailed elaboration of the statistical analyses. The SAP will be finalised before database lock.

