17.1 Sample size calculation

The primary objective of this trial is to compare the efficacy of thrice daily BIAsp 30 versus twice daily BIAsp 30, both in combination with metformin, in subjects with type 2 diabetes inadequately controlled on basal insulin combined with OADs. The primary endpoint is change from baseline in HbA_{1c} after 24 weeks of treatment and the sample size is determined based on this endpoint.

Let D be the mean treatment difference for change in HbA_{1c} (BIAsp 30 TID minus BIAsp 30 BID). The null-hypothesis will be tested against the alternative hypothesis as given by

$H_0: D = 0\%$ against $H_A: D \neq 0\%$

Sample size is determined using a t-statistic under the assumption of a two-sided test and a significance level of 5%. Based on experience from previous trials^{19,20}, an estimated treatment difference of 0.3% and a standard deviation (SD) of 1.1% for HbA_{1c} will be used in the sample size calculation (see [Table 17-1](#)). The randomisation scheme will be 1:1. The sample size calculation is done using Statistical Analysis System (SAS) 9.3.

Table 17–1 Number of subjects required totally under different SD and different power requirement

Subjects in total	Estimated SD in HbA _{1c} (%)			
	1.0	1.1	1.2	1.3
Power				
80%	352	426	506	592
85%	402	486	578	678
90%	470	568	676	792
95%	580	702	834	978

Assuming a SD of 1.1%, a total of 426 subjects (213 subjects per group) in the FAS analysis set will give 80% power in detecting the treatment difference between BIAsp 30 TID and BIAsp 30 BID based on the primary endpoint.

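### The week-24 7-point SMPG profile model leaves the Visit 14 profiles out, so its time-point differences can be biased if glucose-related withdrawal differs by arm

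*Combined protocol and SAP*

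**What the plan says.** Section 8.3.1.2 sets the collection: "The 7-point SMPG profile should be performed on the day just prior to Visit 2, Visit 14 and Visit 26". These visits are baseline, week 12 and week 24.

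Section 17.4.1.1 gives the raw profile its own model: "To compare the 7-point SMPG profiles of the two treatments after 24 weeks, a mixed effect model will be fitted to the data". The fixed effects are treatment, time, their interaction, the combined stratification factor and region. Time means the planned measurement times within the day, and the unstructured covariance is within subject over those times. Neither visit nor baseline glucose appears.

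The next paragraph of that section treats the remaining continuous endpoints differently. Change in FPG and the "endpoints derived from 7-point SMPG profile, will be analysed with a similar method as the primary endpoint", with the relevant baseline value in place of baseline HbA1c.

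The opening of Section 17 rules out imputing missing efficacy values unless specified, and nothing is specified for the profile. Section 6.1 plans 426 randomised and 340 completing. Section 17.3 says: "The main reasons for withdrawal/discontinuation are expected to be ineffective therapy and adverse events". It regards the first of these reasons as missing at random only in part, and doubts that assumption for the second.

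**The concern.** A missing-at-random argument protects a week-24 estimate only if the model conditions on the earlier data that predict withdrawal. The primary MMRM does so for HbA1c. The profile model conditions on neither the Visit 14 nor the Visit 2 glucose values, although both are collected.

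Suppose subjects with high week-12 glucose leave more often in one arm. Those who remain in that arm then have a week-24 profile that looks better than the arm's true profile, and the between-arm difference shifts. The trial is open-label, with a different injection frequency and titration scheme by arm (Sections 5.2 and 5.3.1, Appendix A), so unequal withdrawal is possible.

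The exposure is greatest at the pre-meal and bedtime points. The post-meal values also have MMRM-type analyses as PPG endpoints; the pre-meal and bedtime values have none of their own.

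**Working it through.** **1. The plan's own figure.** No figure is given for the profile model. The one related figure is for the primary endpoint: "Assuming a SD of 1.1%, a total of 426 subjects (213 subjects per group) in the FAS analysis set will give 80% power". A two-sided 5% t-test with difference 0.3 and 213 per arm has 80.2% power by the noncentral t, so 426 reproduces. It says nothing about SMPG.

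**2. What enters the model.** Putting Visit 14 values into a model without a visit term would average weeks 12 and 24, against the stated 24-week target. Visit 26 profiles alone are therefore the response. This is inferred from the model terms; no sentence says it outright. A subject with even one Visit 26 value still contributes.

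**3. Expected loss.** 426 - 340 = 86, and 86/426 = 20.2%.

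**4. Form of the bias.** Assume equal SDs at Visits 14 and 26 and correlation ρ between them. In an arm, let a fraction p leave after Visit 14, and let the leavers' mean Visit 14 glucose exceed the arm mean by δ. The stayers' Visit 26 mean is then off by -ρδp/(1-p). For TID minus BID:

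bias = ρ[δ(BID)·p(BID)/(1-p(BID)) - δ(TID)·p(TID)/(1-p(TID))]

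For each 1 mmol/L of δ, taken equal in both arms, with ρ from 0.3 to 0.7:

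- BID 26%, TID 14%: 0.26/0.74 - 0.14/0.86 = 0.351 - 0.163 = 0.19, so the bias is +0.06 to +0.13 mmol/L.
- BID 16%, TID 24%: 0.190 - 0.316 = -0.125, so the bias is -0.04 to -0.09 mmol/L.
- Equal rates: the terms cancel and the bias is 0.

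**5. Simulation.** The documents give no SMPG SD, no between-visit correlation and no dropout by arm, so all of these are assumptions.

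*Seven-point profiles, 200,000 per arm.* SD 2.0-3.0 mmol/L, correlation 0.3-0.7, withdrawal after Visit 14 depending on mean Visit 14 glucose.

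| Withdrawal | Bias, Visit 26 only (mmol/L) |
|---|---|
| Completely random, or same rate and mechanism in both arms | about 0 |
| Same mechanism, 26% BID vs 14% TID | 0.05 to 0.18 |
| 20% per arm, glucose-dependent in BID only | 0.08 to 0.29 |
| 20% per arm, opposite dependence in the two arms | 0.17 to 0.59 |

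Modelling Visits 14 and 26 jointly left at most about 0.02 in every row, which is simulation noise.

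*One time point, 4,000 trials of 213 per arm.* True difference -0.6, SD 2.2, baseline correlation 0.35, Visit 14-26 correlation 0.4 or 0.6, 8-10% leaving before week 12, later withdrawal logistic in Visit 14 glucose. With about 26% BID versus 14-15% TID:

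- Visit 26 only: -0.43 to -0.53, a shift of 0.07 to 0.17, with 95% CI coverage of 89.5% to 94%.
- Visit 26 plus baseline: -0.46 to -0.55.
- Visits 14 and 26: -0.60, with coverage of about 95.5%.

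With the split reversed (16% versus 24%), Visit 26 only gives -0.65 to -0.67, an overstatement. With equal dropout the bias is 0.01 to 0.02.

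**6. When Visit 14 is not the driver.** Let late withdrawal depend on week-18 glucose, which no 7-point profile records. In one run of the one-time-point setting, Visit 26 only gave -0.49 and -0.44 (correlation 0.4 and 0.6), adding Visit 14 gave about -0.53, and adding baseline as well gave about -0.54. A second run left the Visit 14 estimate at about -0.49. Against a true -0.6, a bias of 0.06 to 0.11 remains.

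**The case against.** A reader might infer that this is a completers-only analysis to which withdrawn subjects add nothing. The documents do not establish that. Section 8.1.7 asks the investigator to aim for Visit 26-type procedures at withdrawal, and Section 18.4 keeps and uses data from the end-of-trial visit. A withdrawn subject may therefore have a late profile. What is missing is a rule on whether it counts as week 24; if it did, the comparison would mix week-24 and earlier values. This objection stands, and the fix includes that rule.

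A reader might also infer that the week-24 differences are biased, or biased against TID. Neither follows. No arm-specific dropout is given, and reversing the assumed split reverses the sign.

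It is tempting to say that the Visit 14 profile corrects the bias. In the simulations that recover the true value, withdrawal was generated from Visit 14 glucose, so full recovery is built in. Step 6 shows partial recovery otherwise, and Section 17.3 itself doubts missing-at-random for adverse events. Visit 14 also cannot help with subjects who leave before week 12.

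Finally, the post-meal points would receive two different week-24 estimates, one from the profile model and one from the PPG models. That alone is not evidence of missing-data bias: the PPG models adjust for baseline and the profile model does not, so the two would differ even with complete data.

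What survives is the omission itself: relevant data are collected, used for the derived endpoints, and left out here.

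**Conclusion.** The point holds as a conditional weakness of one supportive secondary endpoint. It is not among those marked as key in Section 4.2.2.1, and the primary HbA1c analysis is untouched. A working range for the bias is 0.05 to 0.2 mmol/L, under a common glucose-related mechanism, dropout of 26% versus 14-15%, SD 2.0-3.0 and between-visit correlation 0.3-0.7. Larger values need the mechanism itself to differ between arms. The overall 20.2% non-completion follows from Section 6.1; its split by arm and its link to glucose are assumptions. The reading that only week-24 profiles enter rests on the model terms and the stated 24-week target.

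**What to change.** Either of two changes to Section 17.4.1.1, or to an SAP finalised before database lock as Section 17 allows:

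- **Per time point.** Estimate the week-24 difference at each of the seven points with the MMRM already planned for the derived SMPG endpoints: Visits 14 and 26 as responses and the matching Visit 2 value as covariate. Keep the existing joint profile model for the treatment-by-time parallelism test, because seven separate models cannot supply it. That test would still rest on week-24 profiles alone.
- **One joint model.** Add treatment-by-time-by-visit terms (with the lower-order visit terms) and the matching baseline value, with a direct-product covariance over time of day and visit. Take both the parallelism test and the differences as Visit 26 contrasts.

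In either case, state that profiles from early withdrawal visits are not counted as week 24.

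The cost is a few sentences and slightly more programming; no new data are needed. The joint model constrains the covariance: a direct product has 28 + 3 - 1 = 30 parameters, against 14 × 15/2 = 105 for a full 14 × 14 unstructured matrix. The change removes the bias only when withdrawal depends on the observed Visit 2 and Visit 14 glucose; otherwise it reduces it, and the report should say so.

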6.1 Number of subjects

Number of subjects planned to be screened (i.e. documented informed consent): 610

Number of subjects planned to be randomised: 426

Number of subjects expected to complete the trial: 340

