Presentation of results from a statistical analysis of a continuous endpoint analysed by a mixed model for repeated measurements (MMRM) analysis will include the estimated mean (= Least Square Mean) change from baseline for each treatment as well as the estimated mean treatment difference including a two-sided 95% confidence interval and a p-value for test of no difference between treatments.

If an assessment has been made both at screening and randomisation, and if not otherwise specified, the value from the randomisation visit will be used as the baseline value. If the value measured at the randomisation visit is missing and the assessment also has been made at screening, then the screening value will be used as the baseline value. If an assessment is only made at randomisation or at screening the relevant value will be the baseline value.

For efficacy variables missing values will not be replaced by imputed values unless otherwise specified. In the primary analysis missing values are handled by a MMRM.

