The number of treatment emergent severe or BG confirmed hypoglycaemic episodes will be analysed by a negative binomial regression model with a log-link function and the logarithm of the time period in which the hypoglycaemic episodes are considered treatment emergent as offset. The model will include treatment, combination of the two stratification factors and region as factors. The results will include the 95% confidence interval for the event rate ratio (BIAsp TID over BIAsp BID) and p-value as part of the presentation. To the extent where data allow, analyses will be performed on all severe or BG confirmed episodes and nocturnal severe or BG confirmed episodes separately.

Vital signs

Vital signs (systolic blood pressure, diastolic blood pressure and pulse) will be summarised and tabulated by treatment and visit together with the change from the baseline to end-of-treatment.

Laboratory assessments

All continuous laboratory parameters will be evaluated by descriptive statistics and tabulated by visit together with change from baseline to end-of-treatment. Shift tables showing changes from baseline to end-of-treatment (normal and abnormal) will be constructed for each laboratory safety variable. No formal statistical analyses of laboratory parameters will be performed and abnormal values will be listed.

Eye examination and physical examination

For eye examination and physical examination, a shift table for change from baseline to end-of-treatment will be generated. Subjects with any change in examination result will be listed.

Change in body weight after 24 weeks of treatment

Change from baseline in body weight after 24 weeks of treatment will be analysed with a similar method as the primary endpoint, where baseline body weight will replace baseline HbA_{1c} in the model.

Total daily insulin dose

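### The week-24 7-point SMPG profile model leaves out the Visit 2 profile, although every other modelled continuous endpoint is adjusted for its own baseline

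*Combined protocol and SAP*

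**What the plan says.** Section 17.4.1.1 gives the profile its own analysis: "To compare the 7-point SMPG profiles of the two treatments after 24 weeks, a mixed effect model will be fitted to the data". The terms are stated in full: "The model will include treatment, time, interaction between treatment and time, combination of the two stratification factors and region as fixed effects". The within-subject covariance is unstructured. On the meaning of time, the section says: "The time corresponds to planned measurement times during the 24h period". Time is therefore a point within the day and not a visit, so the Visit 2 profile does not enter as a response either.

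The baseline data exist. Section 8.3.1.2 states: "The 7-point SMPG profile should be performed on the day just prior to Visit 2, Visit 14 and Visit 26".

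The other modelled continuous endpoints are handled differently:

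- HbA1c (Section 17.3) has baseline HbA1c as a covariate.
- FPG and the endpoints derived from the SMPG profile (Section 17.4.1.1) use the primary-type model, "where the relevant baseline value will replace baseline HbA_{1c} in the model".
- Body weight (Section 17.4.1.2) uses the same approach, "where baseline body weight will replace baseline HbA_{1c} in the model".

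Vital signs, laboratory values, insulin dose and DTSQs are only described, so they are not part of this comparison.

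**The concern.** The profile is the one modelled continuous endpoint without its own baseline, and the plan does not say why. That the endpoint is a level and not a change does not explain it. Fluctuation in the profile is not a change endpoint either, yet Section 17.4.1.1 adjusts it for its log-transformed baseline.

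The stake is precision at each time point. The three 2-hour post-meal points also have baseline-adjusted estimates through the PPG endpoints, and pre-breakfast glucose is partly covered by laboratory FPG. Pre-lunch, pre-evening-meal and bedtime glucose are compared as levels at that time only in this model. Pre-lunch is of particular interest because Appendix A (Tables 1 and 2) uses it for titration in the TID arm but not in the BID arm.

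**Working it through.** **1. The plan's own figure.** The only sample size given is for HbA1c. A two-sided two-sample t-test with difference 0.3, SD 1.1, alpha 5% and 1:1 allocation gives 426 subjects (power 80.2% at 213 per arm), as in Table 17-1. There is no SD, correlation or power for SMPG, so the effect of the omission has to be expressed over an assumed range.

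**2. Inputs.** Section 6.1 states "Number of subjects expected to complete the trial: 340", which is 170 per arm. Two quantities are assumed:

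- r, the correlation between the Visit 2 and week-24 readings at the same time point: 0.2 to 0.5.
- s, the correlation of SMPG with the two-level HbA1c stratum, taken as equal at both visits: 0.1 to 0.3.

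**3. Gain from adjustment at one time point (ANCOVA approximation).** Ignoring the stratum, the variance is multiplied by 1 − r², so the interval narrows by 1 − √(1 − r²). This is an upper bound. Allowing for the stratum, r is replaced by rp = (r − s²)/(1 − s²). The equivalent increase in subjects is rp²/(1 − rp²). Ranges run from s = 0.3 to s = 0.1.

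| r | Upper-bound narrowing | rp | Narrowing given stratum | Equivalent extra subjects |
|---|---|---|---|---|
| 0.2 | 2.0% | 0.121–0.192 | 0.7–1.9% | 1.5–3.8% |
| 0.3 | 4.6% | 0.231–0.293 | 2.7–4.4% | 5.6–9.4% |
| 0.4 | 8.3% | 0.341–0.394 | 6.0–8.1% | 13.1–18.4% |
| 0.5 | 13.4% | 0.451–0.495 | 10.7–13.1% | 25.5–32.4% |

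With 170 per arm, the unadjusted half-width is 1.96 × √(2/170) = 0.213 SD. Adjusted, and ignoring the stratum, it is 0.203 SD at r = 0.3 and 0.184 SD at r = 0.5.

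**4. Chance imbalance.** The baseline difference at one time point has a 95% range of ±1.96 × √(2/170) = ±0.213 SD. About r times this carries into the unadjusted week-24 difference: 0.043, 0.064, 0.085 and 0.106 SD for r = 0.2, 0.3, 0.4 and 0.5.

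**5. Missing Visit 2 values.** The general baseline rule in Section 17 falls back on the screening value: "If the value measured at the randomisation visit is missing and the assessment also has been made at screening". It cannot help here, because no 7-point profile is taken at screening. If a share m of subjects is dropped for a missing baseline, the variance factor is (1 − rp²)/(1 − m). The gain is cancelled at m = rp²: 1.5–3.7%, 5.3–8.6%, 11.6–15.5% and 20.3–24.5% for the four values of r.

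If the missing baseline is set to the pooled mean instead, the factor is 1 − (1 − m)rp², so 90% of the variance gain remains at m = 10%. For r = 0.3, s = 0.2 and m = 10%, rp = 0.26/0.96 = 0.271 and rp² = 0.0733:

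- none missing: √0.9267 = 0.963, or 3.7% narrower
- dropped: √(0.9267/0.9) = 1.015, or 1.5% wider
- pooled mean: √(1 − 0.9 × 0.0733) = 0.966, or 3.4% narrower

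**The case against.** The strongest case is that this is a preference and not an error. Under randomisation the unadjusted week-24 comparison is unbiased with valid intervals, and the HbA1c stratum, OAD stratum and region are already in the model. The model also has a purpose of its own, to test whether the two profiles are parallel. All of this is correct. No gain is calculated here for the treatment-by-time test.

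Existing coverage is also wider than the 2-hour PPG points and FPG. The mean of the profile uses all seven points and is baseline-adjusted. On the usual definition of a PPG increment (post-meal minus pre-meal, which the plan does not spell out), pre-lunch and pre-evening values enter adjusted analyses through it. This reduces the weight of the point, but neither endpoint estimates the level at a given time of day.

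Precision and chance imbalance must not be counted as two costs. Unadjusted minus adjusted variance is r² × SD² × 2/170. Its 95% range, 1.96 × r × √(2/170) SD, is exactly the carried imbalance in step 4, so the unadjusted interval already contains it. This stands.

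Finally, r may be low. Each point is a single home reading, basal insulin and other OADs stop at randomisation, and all subjects are then titrated weekly to one pre-meal target. At r = 0.2 to 0.3 the gain is about 1–4%. That limits the size, but nothing is lost by adjusting if subjects with a missing baseline are kept.

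**Conclusion.** The point holds. The term list is complete and has no baseline SMPG, the data are collected, and no other section supplies the term or a reason for leaving it out. Intervals at each time point are wider than they need be. Adjustment would narrow them by about 1–2% at r = 0.2 and 11–13% at r = 0.5, given the stratum already in the model. These figures rest on assumed values of r and s and on a single-time-point approximation; the reading of the text does not.

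The consequence is modest. It concerns efficiency, not validity, on a supportive secondary endpoint that is not among those marked as key in Section 4.2.2.1. The change is still worth making because it costs almost nothing and brings this model into line with the rest of the plan.

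**What to change.** In Section 17.4.1.1, add two terms to the profile model: the Visit 2 SMPG value at the same time point, and its interaction with time, so that each of the seven points has its own slope. Keep the unstructured covariance. Add a rule that keeps subjects with a missing Visit 2 value, for example by setting the baseline covariate to the mean at that time point pooled over both arms. If the omission is deliberate, state the reason.

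The cost is two model terms and one sentence on missing baselines. No new data, visits or subjects are needed. Section 17 allows a SAP to be finalised before database lock, and the change could be written there.
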